11.5.4.2 Analysis of PD ligand expression (Qualtek analysis)

- a. Formalin-fixed tissue will be utilized for analysis of PD-L1 and PD-L2 using commercially available reagents from the Dako EnVision FLEX+ HRP-Polymer kit (DAKO K8012; Dako, Carpinteria, CA) and the 22C3 antibody.
- b. Briefly, slides will be baked at 60°C, deparaffinized in xylenes, and rehydrated with graded ethanols to distilled water.
- c. Antigen retrieval will be performed using the Dako EnVision FLEX Target Retrieval Solution, low pH (supplied as a citrate-based buffered solution, pH 6.1) in a steamer.
- d. Cooled slides will be stained using the automated TechMate IHC staining platform including an additional Proteinase-K antigen retrieval step (Dako #S3020)
- e. The 22C3 antibody will be diluted at 2 µg/mL in Dako Primary Antibody Diluent for off-platform overnight incubation in a dark humidified chamber.
- f. The EnVision FLEX+ Polymer reagents will be utilized for primary antibody detection including the mouse linker, HRP-polymer, DAB chromogen and DAB enhancer.
- g. EnVision FLEX+ wash buffer will be used between incubation steps, with slides counterstained with hematoxylin.
- h. Slides will then be rinsed in distilled water and subjected to an ethanol dehydration series and xylene changes before coverslipping.

11.5.4.3 Measurement of antigen-specific T cells and evaluation of cellular functionality by intracellular cytokine and effector molecule staining

PBMCs derived from Green Top tubes and flash frozen tumor tissue will be utilized for evaluation of cellular functionality by cytokine detection after stimulation. Briefly,

- a. Antigen presenting cells (APCs; monocytes, DCs, etc., 1×10^5 cells) will be obtained from PBMCs isolated from Green Top tubes by HLA-DR positive bead selection (Miltenyi Biotec), washed in Aim V media and pulsed at 37°C in a 5% CO₂, humidifying incubator in Aim V media for 1 hour with tumor antigen peptides of interest (gp100, Mart-1, tyrosinase) and washed 3x Aim V media.
- b. Non-APCs from the PBMCs (80-90% T cells) will then be cultured with these loaded cells APCs for 24 hours at 37°C in a 5% CO₂, humidifying incubator (or anti-CD3 stimulation antibody at 1mg/ml [positive control] or unloaded APCs or no APCs [negative controls]. During the last 6 hours in incubation, Golgi Plug [Pharmingen] will be added.
- c. After stimulation cells will be washed 3x in PBS and stained for extracellular antibodies identifying CD8+ cells subsets and intracellular antibodies for cytokines and effector molecules of interest (IFN γ , TNF α , IL-2, granzyme B, perforin, and CD107), according to protocols described in the "Immunophenotypic analysis of immune cells and markers by multiparameter flow cytometry" [REDACTED]

- d. Cells will be analyzed by flow cytometry. Antigen-specific T cells will be defined as cells producing any one of the cytokines or effector molecules of interest, while functionality will be defined by the ability to co-produce combinations of the cytokines or effector molecules of interest.

11.5.4.4 Measurement of antigen-specific T cells by MHC dextramer staining

To measure tumor antigen-specific responses PBMCs from Green Top tubes or extracted from flash frozen tumor tissue of patients found to be HLA-A2-positive by protocols in the "Immunophenotypic analysis of immune cells and markers by multiparameter flow cytometry" section" will be stained with MHC dexamers (including those identifying cells specific against melanoma-specific antigens gp100, MART-1, and tyrosinase, or positive and negative control antigens CMV, EBV, Influenza, HIV, and empty). Specifically:

- a. PBMCs from Green Top tubes and processed tissues will be thawed quickly by immersion of the bottom 90% of the cryovial in a 37°C water bath and washed once in PBS (with centrifugation and reconstitution of the cell pellet in 50 µl PBS per sample) prior to dextramer staining.
- b. As per manufacturer instructions, 10-20 µl of tetramer will be added to the cells and incubated for 30 min in the dark at room temperature.
- c. Thereafter, the ECS protocol described above will be followed to determine CD8+T cells (and exclude B, monocyte/macrophage, and dendritic cells from dextramer analysis).

11.5.4.5 Serological assays to evaluate antibody titers to tumor-associated antigens

Serum from Red Top tubes will be thawed for analysis of antibody titers to tumor associated antigens. Briefly:

- a. Tumor-associated antigens (gp100, MART-1, and tyrosinase) will be prepared within PBS for plate well coating (200 µl per well of 96 well plate) and incubated at 37 °C for 30 min., or incubated (covered) overnight at 4 °C.
- b. The coating solution will be removed and the plate washed 3x with PBS prior to the additional blocking step (30 min. 5% BSA-PBS) Dilute the monoclonal primary antibody in PBS. The optimal dilution should be determined using a titration assay.
- c. Then 0.2 ml of the diluted monoclonal antibody will be added to each well. The negative control will be a species- and isotype-matched, non-specific immunoglobulin diluted in PBS.
- d. The plate will be incubated at room temperature for 2 hours, washed 3x in PBS, followed by addition of the secondary antigen (0.2 ml per well).
- e. The plate will be incubated at room temperature for 2 hours, washed 3x in PBS, and the freshly prepared enzyme substrate will be added (0.2 ml of the freshly prepared substrate to each well).

- f. Color development will be observed (expected after 30 min of incubation at room temp) and absorbance will be read (at 405 nm) immediately in a microplate reader or the reaction will be stopped with 50 µl per well of the appropriate stopping reagent and absorbance read within 2 hours.

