	
interventions (transfer to a higher level of care, use of vasopressor, or use of supplemental oxygen) will be summarized.
 
 • Clinical measures of efficacy will be described, including overall survival, progression-free survival, need for additional therapy. • Descriptive statistical will be used, except where otherwise specified. Continuous variables will be presented by summary statistics (such as mean, median, standard error and 90% CI) and the categorical variables by frequency distributions (i.e., frequency counts, percentages and 90% CI). 
Analysis of Exploratory Objectives
 
 • Evaluation of immunological responses will be primarily based on the breadth and magnitude of cellular responses. The frequency of tumor specific T cells and regulatory cells including CD4+ Tregs and effector CD8+ will be measured pre-treatment and various days post-treatment in the tumor, when possible, and peripheral blood. Treatment effect for each patient will be measured as paired differences between pre and post measurements of these parameters at various times. Transformation of the data will be performed if appropriate, e.g. log transformation, and hence treatment effect will be expressed on a log scale.

Correlative Studies
	
Tumor Microenvironment
 
 • PD-L1 staining • Frequency of effector CD8+ T cells • Frequency of CD4+FoxP3+ regulatory T cells 
Peripheral Blood
 
 • Analysis of lymphocyte and myeloid cell subpopulations using flow cytometry • Chemokine/cytokine measurements • Serum VEGF, fibronectin, and CRP levels • Melanoma antigen specific T cell responses and antibodies

Number of trial subjects
	
60-65

Estimated enrollment period	24 months
Estimated duration of trial	36 months
Duration of Participation	Up to 2 years

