11.5.4.6 Multiplex cytokine analysis

Serum from Red Top tubes will be thawed for analysis of cytokines using the Bio-Plex Cytokine Assay (BioRad). Briefly:

- a. Thawed serum samples will be prepared for by diluting 1 volume of the serum sample with 3 volumes of the Bio-Plex human serum sample diluent. Extremely lipemic samples should be filtered through a 0.22 µm filter to prevent clogging.
- b. The cytokine standard dilutions will be prepared as per manufacturer instructions from the manufacturer's master standard stock, for the cytokines of interest, including IFN α , IFN β , IFN γ , IL-1 β , IL-2, IL-4, IL-6, IL-8, IL-10, IL-12p70, and TNF-alpha.
- c. A multiplex bead working solution will be prepared from the anti-cytokine conjugated 25x beads and the multiplex plate will be prepared using Bio-Plex assay and wash buffers.
- d. Diluted standard or serum-derived samples will be pipetted (50 µl each) per well, sealed within the plate, and incubated on a microplate shaker for 30 min at room temperature.
- e. The wells will be washed with Bio-Plex wash buffer (100 µl; 3x), and detection antibody solution (0.5 µl/well) will be added to the wells, sealed within the plate, and incubated on a microplate shaker for 30 min (1,100 rpm for 30 sec and 300 rpm at room temperature for the remainder of the incubation).
- f. 300 rpm at room temperature for the remainder of the incubation).
- g. The wells will be washed with Bio-Plex wash buffer (100 µl; 3x), and pre-diluted streptavidin-PE (1x; 50 µl/well) will be added to each well, sealed within the plate, and incubated on a microplate shaker for 10 min (1,100 rpm for 30 sec and 300 rpm at room temperature for the remainder of the incubation) at room temperature.
- h. The wells will be washed with Bio-Plex wash buffer (100 µl; 3x), and Bio-Plex assay buffer will be added (125 µl/well) to the wells, sealed within the plate, and incubated on a microplate shaker for 30 seconds (1,100 rpm) at room temperature.
- i. The plate will be analyzed on a Bio-Plex array reader, as per the manufacturer instructions within 1 hour of last incubation.

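### The written antibody-titer assay (section 11.5.4.5) never adds patient serum to the plate: the primary layer it names is a monoclonal antibody

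*Combined protocol and SAP*

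**What the plan says.** The synopsis (SAP, section 1.0, Correlative Studies, peripheral blood) lists "Melanoma antigen specific T cell responses and antibodies". Section 11.5.4.5 of the combined protocol and SAP gives the bench procedure for the antibody part, and its opening names the sample: "Serum from Red Top tubes will be thawed for analysis of antibody titers to tumor associated antigens".

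The steps then run as follows:

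- Step a coats the plate: "Tumor-associated antigens (gp100, MART-1, and tyrosinase) will be prepared within PBS for plate well coating".
- Step b washes and blocks the wells, and instructs: "Dilute the monoclonal primary antibody in PBS". The working dilution of that antibody is to be found by titration.
- Step c loads the wells: "Then 0.2 ml of the diluted monoclonal antibody will be added to each well". It also sets the control: "The negative control will be a species- and isotype-matched, non-specific immunoglobulin diluted in PBS".
- Step d incubates and washes, "followed by addition of the secondary antigen (0.2 ml per well").
- Step e incubates, washes and adds enzyme substrate.
- Step f reads absorbance at 405 nm, either at once or after a stopping reagent.

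**The concern.** A serum titer assay on an antigen-coated plate measures antibody in the patient's serum, so that serum has to be the layer placed on the antigen. Here the layer named is a reagent antibody. Such an antibody gives the same binding whichever patient's serum has been thawed, apart from assay noise. A laboratory working strictly from these steps would use up plates, and possibly serum aliquots, and obtain no patient data on melanoma-antigen antibodies.

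What is at stake is one exploratory correlative measurement. It serves the objective in section 3.3, which seeks immune features that correlate with response as candidate predictive biomarkers.

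**Working it through.** The plan gives no figure to reproduce and no formula applies. The check is to trace what enters the well at each step, then compare that with the section's purpose and with the neighbouring serum assay.

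**Contents of the well, section 11.5.4.5**

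| Step | What enters the well | Patient serum? |
|---|---|---|
| a | gp100, MART-1 and tyrosinase as coating | No |
| b | Blocking buffer (the monoclonal antibody is diluted separately) | No |
| c | Diluted monoclonal antibody, or the isotype-matched control | No |
| d | Secondary reagent, named as an antigen | No |
| e | Enzyme substrate | No |
| f | Stopping reagent if used; absorbance read | No |

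Serum enters at 0 of 6 steps.

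**Could the monoclonal antibody have another role?**

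- As a positive control only: no, because it goes into each well.
- As the detection layer: no, because it is called the primary antibody and a secondary reagent follows in step d.

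**Do the surrounding details fit a serum assay?**

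- Titration in step b finds one working dilution of a reagent. A titer is read from dilutions of the sample, and the section gives no serum dilution, titer definition or positivity cut-off.
- A species- and isotype-matched immunoglobulin is the right control for a monoclonal reagent. Patient serum is polyclonal and needs a control serum, and none is named.
- The substrate in step e implies an enzyme-linked secondary antibody, so calling the step d reagent an antigen is a further slip in the same lines.

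Taken together, steps b and c describe an assay that probes for antigen with a monoclonal antibody, not one that measures antibody in serum.

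**Comparison with the next section.** Section 11.5.4.6 (multiplex cytokine analysis) also starts from thawed Red Top serum and is also offered as a brief description. It nevertheless gives the serum dilution (1 volume of serum to 3 of diluent) and the loading step: "Diluted standard or serum-derived samples will be pipetted". The appendix therefore does state sample loading in its abbreviated procedures, and section 11.5.4.5 lacks it.

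**Is it put right elsewhere?** Sections 11.5.1.1 and 11.5.2.1 cover collection, separation and storage of serum, not the assay. The reference to laboratory SOPs in section 11.5.4.8 applies to the additional analyses described there. Sections 7.1.4 (correlative blood sampling) and 8.8 (exploratory analysis) appear in the table of contents but were not in the text available for this review, so a correction there cannot be excluded.

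**The case against.** The best reply is that the intent is plain. The heading calls this a serological assay, the first sentence says serum is thawed for it, and the steps are introduced as a brief account. The appendix is loosely edited in general: section 11.5.4.4 moves between dextramer and tetramer, and section 11.5.4.6 repeats a sentence fragment as a separate step. On this view the passage is one more slip, and a competent laboratory would add serum anyway.

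Most of that stands. It makes a drafting error the likeliest explanation, and the point is limited to the procedure as written. It does not rescue the text. Brevity can excuse an omitted detail, but here a primary reagent is named, its control matches it, and both are wrong for a serum titer.

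A reader might also infer three stronger things that the documents do not support:

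- **That a trial endpoint is lost.** The synopsis lists its study endpoints separately, and antibodies are not among them. They appear under correlative studies.
- **That a planned pre/post analysis of antibodies is lost.** The paired analysis in the synopsis follows a sentence about tumor-specific T cells and regulatory cells. Extending it to antibody titers may be reasonable, but it is inference.
- **That the trial's serology will in fact show no signal.** That would require a laboratory to thaw serum for a titer assay and never plate it. The text shows only that the written steps omit the sample, and only in this assay. The cytokine assay, which uses the same type of serum tube, does state its loading step.

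**Conclusion.** The point holds as an error in the written laboratory procedure. Section 11.5.4.5 promises a titer in patient serum and describes an assay in which patient serum is never plated. If the steps were followed literally, every reading from this assay would be independent of the patient's antibodies, and the exploratory study of melanoma-antigen antibodies would be uninformative.

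The size is small. One exploratory correlative assay is affected. Nothing in the response-rate endpoint, the safety evaluation, the sample size or the criteria for a positive trial depends on it.

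The conclusion assumes that steps a to f are the operative instructions and that nothing in sections 7.1.4 or 8.8, or in a laboratory document outside the plan, corrects them. If such a correction exists, what remains is an inconsistency to tidy up.

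**What to change.** Rewrite steps b to d of section 11.5.4.5 so that:

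1. diluted patient serum is the primary layer added to the coated, blocked wells;
2. the second reagent is an enzyme-linked secondary antibody against human immunoglobulin, replacing the reference to an antigen;
3. any monoclonal antibody to the coated antigens is a positive control in designated wells only;
4. a suitable negative-control serum replaces the isotype-matched immunoglobulin;
5. the text states the serum dilutions and how titer is read from them.

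Running a patient's baseline and later samples on the same plate would be good practice, since it keeps plate-to-plate variation out of within-patient comparisons. It is an optional addition and not part of the error.

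The cost is a few lines in a laboratory appendix, with no change to sampling, visits, sample size or the clinical analyses. If the laboratory already runs the assay on serum, the amendment only brings the text into line with practice.

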11.5.4.6 Multiplex cytokine analysis

Serum from Red Top tubes will be thawed for analysis of cytokines using the Bio-Plex Cytokine Assay (BioRad). Briefly:

- a. Thawed serum samples will be prepared for by diluting 1 volume of the serum sample with 3 volumes of the Bio-Plex human serum sample diluent. Extremely lipemic samples should be filtered through a 0.22 µm filter to prevent clogging.
- b. The cytokine standard dilutions will be prepared as per manufacturer instructions from the manufacturer's master standard stock, for the cytokines of interest, including IFN α , IFN β , IFN γ , IL-1 β , IL-2, IL-4, IL-6, IL-8, IL-10, IL-12p70, and TNF-alpha.
- c. A multiplex bead working solution will be prepared from the anti-cytokine conjugated 25x beads and the multiplex plate will be prepared using Bio-Plex assay and wash buffers.
- d. Diluted standard or serum-derived samples will be pipetted (50 µl each) per well, sealed within the plate, and incubated on a microplate shaker for 30 min at room temperature.
- e. The wells will be washed with Bio-Plex wash buffer (100 µl; 3x), and detection antibody solution (0.5 µl/well) will be added to the wells, sealed within the plate, and incubated on a microplate shaker for 30 min (1,100 rpm for 30 sec and 300 rpm at room temperature for the remainder of the incubation).
- f. 300 rpm at room temperature for the remainder of the incubation).
- g. The wells will be washed with Bio-Plex wash buffer (100 µl; 3x), and pre-diluted streptavidin-PE (1x; 50 µl/well) will be added to each well, sealed within the plate, and incubated on a microplate shaker for 10 min (1,100 rpm for 30 sec and 300 rpm at room temperature for the remainder of the incubation) at room temperature.
- h. The wells will be washed with Bio-Plex wash buffer (100 µl; 3x), and Bio-Plex assay buffer will be added (125 µl/well) to the wells, sealed within the plate, and incubated on a microplate shaker for 30 seconds (1,100 rpm) at room temperature.
- i. The plate will be analyzed on a Bio-Plex array reader, as per the manufacturer instructions within 1 hour of last incubation.

11.5.4.7 Nanostring Gene Expression Analysis

RNA from preservation media will be utilized for gene expression analysis using the Nanostring nCounter System. Briefly:

- a. Extracted total RNA will be further purified using RNeasy mini spin columns (Qiagen) according to the manufacturer's protocol. The [REDACTED]

- of the total RNA preparation will be determined by measuring absorbance at 260 and 280 nm using the Nanodrop system (Thermo Scientific).
- b. Each hybridization reaction will require 100-150 ng of total RNA. The integrity of the total RNA preparation will be verified on a Bioanalyzer (model 2100, Agilent Technologies) before proceeding with the hybridization reaction. RNA should be aliquoted (to avoid freeze/thaw cycles) and stored for up to several years at -80°C .
 - c. Hybridization of the target mRNA to the gene-specific probe pairs will be carried out in triplicate with each sample containing 5 μl RNA (150 ng), 10 μl reporter probe (final 40 pM), 5 μl capture probe (final 200 pM), and 10 μl hybridization buffer ($5\times$ SPPE, pH 7.5, with 0.1% Tween-20).
 - d. Using a thermocycler, the hybridization reaction will be conducted will be at 65°C for optimally 16 h (at least 12 h but not more than 30 h).
 - e. After the hybridization reactions are completed, post-hybridization processing will immediately continue using the nCounter Prep Station, as per the manufacturer instructions on using the instrument.
 - f. After post-hybridization processing, the nCounter Digital Analyzer will be used to acquire images of the immobilized fluorescently labeled target mRNA molecules in the sample cartridge using a CCD camera and a microscope objective lens and the expression level of a gene will be measured and tabulated in a CSV format by the system.
 - g. Using Excel, the individual data files will be imported into a collector file template provided by the analyzer manufacturer. The abundance of target mRNA molecules will be compared across multiple different samples and thus normalized for all target genes in all samples based on the positive spike-in controls to account for differences in hybridization efficiency and post-hybridization processing, including purification and immobilization of complexes.
 - h. To determine if the normalized, background-subtracted counts are statistically above background, a Student's t test will be performed against eight human negative controls. A gene will be considered to be above background if the average count for the target gene is greater than the average counts for the eight negative control genes and if the P value of the t test is less than 0.05.
 - i. The relative changes in the abundance of target mRNA molecules will be calculated using the normalized, background-subtracted counts for one or more reference genes included manufacturer set.

11.5.4.8 Other Analyses

If samples are available, some or all of the following analyses may also be performed: Genetic studies, proteomics, and grafting of fresh tissue into experimental animals using blood and tumor tissue. The experimental protocol will follow laboratory SOPs and published procedures.

11.5.5 Safety Precautions

Universal precautions (*i.e.*, a method of infection control in which all human blood and body fluids are treated as if they are infectious for Hepatitis Viruses, Human Immunodeficiency virus, and other known and unknown infectious agents) will be utilized when handling all unfixed cells and tissues.

- a. Hepatitis B and Hepatitis C viruses may be transmitted through blood and other body fluids, and are associated with acute hepatitis, chronic liver disease, and hepatocellular carcinoma in humans. The probability of seroconversion after needlestick exposure is estimated at 7%. Untreated virus can persist for up to one week at room temperature. All staff who work with human tissue must provide evidence of Hepatitis B vaccination.
- b. Human Immunodeficiency virus (HIV) is a retrovirus that causes severe immunodeficiency. Infection increases the risk of developing malignancies, infection by opportunistic organisms, and death. The probability of seroconversion after needlestick exposure is estimated at 0.5%. Infectivity of untreated virus persists for up to one week at room temperature.
- c. Other potentially infectious agents, both known and unknown, pose hazards to those working with human tissue. Included are tuberculosis, HTLV1, Coccidiomycosis, Creutzfeldt-Jacob disease, amongst others.
- d. Individual institutional and OSHA guidelines must be followed when handling human cells and tissues, and referred to for additional information on bloodborne pathogens, laboratory safety, chemical safety, and biohazardous waste disposal. Briefly:
 - i. Personal protective equipment (PPE) must be used at all times while working with human tissue. These include disposable latex or nitrile gloves, face shield, protective splash-resistant laboratory coat (disposable preferred), and covered protective shoes.
 - ii. Gloves should be immediately removed and replaced in the event that they become torn or perforated. Gloves must be removed prior to leaving the work area, and disposed of in an appropriate waste disposal container. Hands must be washed in a "clean" sink after removal of gloves.
 - iii. Face shields, goggles and masks should be worn whenever a potential for exposure to splashes, spray, splatter, droplets, aerosols of blood or tissue fluid, or other potentially infectious materials may be generated, and if there is a potential for eye, nose or mouth contamination. They should be worn at all times while handling tissue in the for processing.
 - iv. Protective lab coats, preferably disposable types, must be donned while working with tissue. Contaminated clothing must be removed prior to leaving the work area, and appropriately laundered or discarded, as per individual institutional guidelines.
 - v. All waste must be disposed of prior to leaving the work area. Biohazardous sharps must be properly disposed of in an approved "sharps" container. All other non-sharp waste must be disposed of in an approved orange or red biohazardous waste disposal bag.

- vi. After completion of work with human tissue, all work surfaces must be disinfected with a product that has been demonstrated to be effective against bacteria, viruses, pseudomonas, tuberculosis and fungi. Product literature should be referred to for appropriate use.
- e. Any injuries or exposure to human tissue or potentially infectious biologic agents must be reported promptly as specified in individual institutional safety guidelines.

